3.0 ABBREVIATION

AE	adverse event
COI	conflict of interest
CRO	contract research organization
DTSQ	Diabetes Treatment Satisfaction Questionnaire
DTR-QOL	Diabetes Therapy-Related QOL
FDA	US Food and Drug Administration
GCP	Good Clinical Practice
ICH	International Conference on Harmonization of Technical Requirement for Registration on Pharmaceuticals for Human Use
MHRA	Medicines and Healthcare Products Regulatory Agency
MedDRA	Medical Dictionary for Regulatory Activities
QOL	Quality Of Life
SAE	serious adverse event
SAP	statistical analysis plan

4.0 INTRODUCTION

4.1 Background

The aim of diabetes treatment is to maintain Quality of Life (QOL) similar to that of healthy people and continue the same QOL for life as that of healthy people¹⁾. Well controlled blood glucose, lipid and blood pressure levels to prevent complications in the early stages and greatly influence the patients' QOL and prognoses. One of the characteristics of diabetes is a tendency of frequent treatment discontinuation because a patient tends to be unaware of his/her disease even after a diagnosis of diabetes due to limited subjective symptoms during the early stages without notable complications. However, in diabetes treatment, prevention of complications or slow disease progression cannot be expected unless the patient is committed to the treatment; therefore, the key point in diabetes treatment is to improve the patients' QOL to enable continued management of diabetes. On the other hand, discontinuation of diabetes treatment leads to progression of disease complications and poor QOL. Patients' understanding of the treatment and the relationship between patients and medical personnel are important²⁾. The research using an auto-recording system captured medication use reported that the level of compliance is decreased as dosing frequency increased³⁾. In this context, to minimize the dosing frequency (number of tablets) is expected to contribute to the improvement in the QOL and treatment satisfaction.

Dipeptidyl peptidase 4 (DPP-4) inhibitors inhibit degradation of gastrointestinal hormones GIP and GLP-1, and thereby, enhance incretin effects glucose-level-dependently, and consequently decrease blood glucose. In Japan, the first DPP-4 inhibitor was approved in December 2009. Since then, many "daily-dosing" DPP-4 inhibitors have been approved one after another which required to be taken every day. In March 2015, trelagliptin was approved as the world's first "weekly-dosing" DPP-4 inhibitor. In the use of trelagliptin, benefits of improving medication adherence are expected due to less frequent dosing compared with existing oral glucose-lowering medications, especially in patients who are starting oral glucose-lowering monotherapy.

4.2 Rationale for the proposed study

QOL study in patients with type 2 diabetes starting treatment with oral glucose-lowering medications can be expected to provide useful rationales in choosing a therapeutic medication corresponding to various lifestyles of patients. DPP-4 inhibitors, including "daily-dosing" products, have presented limited evidence regarding effects on the QOL of diabetes patients.

Accordingly, this study has been proposed to assess trends in the reduction of treatment burden using the Diabetes Treatment Satisfaction Questionnaire (DTSQ). Also, to assess changes and trends in the QOL at pre- and post-treatment of trelagliptin or a daily DPP-4 inhibitor in diabetes patients solely

controlled by diet/exercise therapy, comparing the "weekly-dosing" product with "daily-dosing" products, using the Diabetes Therapy-Related QOL (DTR-QOL) Questionnaire.

5.0 STUDY OBJECTIVES AND ENDPOINTS

5.1 Objectives

The objective is to assess the reduction in treatment burden during 12 weeks of trelagliptin administration in patients with type 2 diabetes on diet and exercise therapy only.

5.2 Definition of endpoints

5.2.1 Primary endpoints

Change from baseline (Week 0) in total score for all question items in the DTR-QOL Questionnaire at the end of the treatment period (Week 12) .

5.2.2 Secondary endpoints

5.2.2.1 Efficacy assessment:

- Changes in the total score for each factor provided through the DTR-QOL Questionnaire [Factor 1: Burden on social activities and daily activities (13 questions in all), Factor 2: Anxiety and dissatisfaction with treatment (8 questions in all), Factor 3: Hypoglycemia (4 questions in all) and Factor 4: Treatment satisfaction (4 questions in all)] at each assessment time point.
- Change in the total score for all questions in the DTR-QOL Questionnaire at each assessment time point.
- Change in the total score for treatment satisfaction in the Diabetes Treatment Satisfaction Questionnaire (DTSQ) at each assessment time point.
- Changes in the total scores for all questions in the DTR-QOL Questionnaire and the total scores for treatment satisfaction in the DTSQ, stratified by the following factors at the start of the treatment period (Week 0) within each treatment group.
 - Use of medication for treatment of comorbidities
 - Number of daily doses of medication for treatment of comorbidities (<2 times or ≥2 times)
 - Total number of daily tablets of medications for treatment of comorbidities (<2 tablets or ≥2 tablets)
 - Number of doses of the study drug or comparative drug (once weekly, once daily or twice daily)
- Changes in the score per question in the DTR-QOL Questionnaire at each assessment time point.

- Changes in the score per question in the DTSQ at each assessment time point.

5.2.2.2 Safety endpoints

- Adverse events
- Incidence of hypoglycemia
- Hospitalization for type 2 diabetes (duration and number, excluding educational hospitalization without worsening of diabetes)

5.2.3 Other Endpoints

- Laboratory tests [HbA1c, fasting blood glucose, fasting insulin, fasting glucagon, glycoalbumin, 1,5-AG, serum creatinine, urinary 8-OHdG (using a correction value of uric creatinine (8-OHdG/creatinine)) and urinary creatinine]
- Treatment compliance
- The Basic Information on Study Subject (Your Basic Profile)

6.0 CLINICAL STUDY DESIGN

6.1 Clinical study design

<Clinical study design>

This is a multi-center, randomized, open-label, parallel-group comparison study to assess the reduction in treatment burden during the administration of a DPP-4 inhibitor (trelagliptin or a daily DPP-4 inhibitor) for 12 weeks in patients with type 2 diabetes on diet and exercise therapy only.

Eligible study subjects as a result of eligibility assessment after giving informed consent will be randomized to either of the study drug (trelagliptin) group or the comparative drug (daily DPP-4 inhibitor) group as specified in Section 8.4.

< Dosage and Administration>

The study drug group: Trelagliptin 100 mg is orally administered once weekly. Trelagliptin 50 mg is orally administered once weekly in patients with moderate renal impairment.

The comparative drug group: An inhibitor is orally administered at the dosage and administration in the package inserts for each drug.

<Evaluation period and visit frequency for study subjects>

Evaluation period: 16 weeks (Screening period: 4 weeks; treatment period: 12 weeks)

Number of visits: total 4 visits

A study subject will visit to his/her study site at the start of the screening period (Visit 1; Week -4), at the start of the treatment period (Visit 2; Week 0 of the treatment period), during the treatment period (Visit 3; Week 4 of the treatment period) and at the end of the treatment period (Visit 4; Week 12 of the treatment period).

<Planned number of study subjects>

As the number of randomized subjects:

The study drug (Trelagliptin) group 120 subjects

[figure not shown]
The comparative drug (daily DPP-4 inhibitor) group 120 subjects

<Number of study sites>

Approximately 15

Figure 6 (a) shows an outline of the clinical study design. Refer to Appendix A for schedule of examinations, observations, and evaluations.

CONFIDENTIAL

CONFIDENTIAL

Figure 6.a Outline of the clinical study design

<Outline of the clinical study>

Duration of treatment: 12 weeks

Number of visits: 4 visits

6.2 Rationale for the clinical study design

(1) Rationale for the clinical study design

The study was designed as an open-label, parallel-group comparative study, to assess impact of trelagliptin on QOL of type 2 diabetes compared with Daily DPP-4 inhibitors. In conducting this parallel-group comparative study, randomization with stratification will be performed, using "the total score for all factors (1-4) in the DTR-QOL Questionnaire (<80% or ≥80%)" and "HbA1c (<8.0% or ≥8.0%)" as stratification factors, for the purpose of adjusting effects on the reduction level of diabetes treatment burdens in patients controlled by diet/exercise therapy during Visit 1.

(2) Rationale for the study period

The treatment period was designed as 12 weeks, because switch to other treatment including combination therapy with other medications is recommended for a case fails to achieve the therapeutic target following three-month continuous administration, as the evaluation on responses to treatment with oral diabetic medications¹⁾, and in a study which investigate changes in DTR-QOL score during treatment with sodium glucose transporter 2 (SGLT2) inhibitor, statistically significant increase in the score was observed at 12 weeks of treatment and scores at 12 weeks and 24 weeks was comparable.

(3) Rationale for the number of planned study subjects

See Section 13.3.

6.3 Premature termination of entire clinical study or premature termination of clinical study at a study site

6.3.1 Premature termination criteria of entire clinical study

The sponsor should immediately discontinue the study when at least one of the following criteria is applicable:

- When new information or other evaluation on the safety or efficacy of the study drug becomes available that shows a change in the known risk/benefit profile of the concerned compound, and risks/benefits are no longer tolerable for study subject participation in the study.

CONFIDENTIAL

- When there is serious deviation from Ethical Guidelines or ICH-GCP for medical and health study involving human subjects.

6.3.2 Criteria for premature termination of study sites

Termination of involvement of a study site in the study may be requested prematurely at the discretion of the sponsor if the entity (e.g., principal investigator) is found to have significant violation of the ethical guidelines, protocol, or contractual agreement for medical and health study involving human subjects or becomes unable to ensure proper conduct of the study, or otherwise as specified in the contractual agreement.

6.3.3 Procedures of clinical study suspension and premature termination of entire clinical study or clinical study at a study site

In the event that the sponsor or a study site committee such as an Ethical Review Board decides to prematurely suspend or terminate the entire clinical study or clinical study at a study site, a study-specific procedure shall be provided by the sponsor. The procedure shall be followed by applicable study sites during the course of clinical study suspension or premature termination.

6.4 Procedures for protocol revision

If the protocol needs to be revised, the sponsor shall consider and decide whether to revise the protocol.

The principal investigator of each study site shall be informed of the details of each protocol revision. Principal investigators shall confirm the content of the revision of the protocol and submit a letter of agreement to the sponsor as evidence of agreement with the protocol revision.

Upon notification, the principal investigator at each study site shall submit the revised contents to committees such as the Ethical Review Board, as necessary according to institutional regulations for review, and obtain approval from the director of the entity.

7.0 SELECTION AND WITHDRAWAL CRITERIA OF STUDY SUBJECTS

The principal investigator or investigator shall check for all the inclusion/exclusion criteria including the test results prior to randomization.

7.1 Inclusion criteria

Eligibility of study subjects shall be determined in accordance with the following criteria.

1. Patients diagnosed as type 2 diabetes.
2. Patients with a stable diet and exercise therapy only for at least 12 weeks prior to the start of the screening period.
3. Patients who require a DPP-4 inhibitor treatment.
4. Patients with HbA1c $\geq 6.5\%$ and $< 10.0\%$ at the start of the screening period.
5. Patients who completed DTR-QOL questionnaire at the start of the screening period.
6. Patients who have received less than 2 types of medication for treatment of comorbidities (such as hypertension or dyslipidemia) at the start of the screening period (any number of daily doses).
7. Patients who, in the opinion of the principal investigator or the investigator, are capable of understanding the content of the clinical study and complying with the study protocol requirements.
8. Patients who can provide the written informed consent prior to the initiation of any study procedures.
9. Patients aged ≥ 20 years at the time of informed consent.
10. Outpatient.

[Rationale for the inclusion criteria]

1-3: These were set to specify a study subject applicable to achieve objective of this study.

4: The lower and upper limits were set to include a study subject whom treatment with oral glucose-lowering medications is considered to require and who is suitable for glucose-lowering monotherapy.

5: This was set because total score of DTR-QOL questionnaire at the start of the screening period is stratifying factor of randomization.

6: This was set to minimize influences on drug taking behavior by medications for comorbidities in the QOL study.

7-10: These were set as fundamentals for this study.

7.2 Exclusion criteria

Study subjects meeting any of the criteria below shall not be included in this study.

CONFIDENTIAL

1. Patients who are receiving any oral anti-diabetic medication for the treatment of type 2 diabetes at the start of the screening period.
2. Patients diagnosed as type 1 diabetes.
3. Patients with severe renal impairment or renal failure (e.g., eGFR <30 mL/min/1.73 m² or on dialysis).
4. Patients with serious heart disease or cerebrovascular disorder, or serious pancreatic, blood, or other disease.
5. Patients with a history of gastrointestinal resection.
6. Patient with a proliferative diabetic retinopathy.
7. Patient with malignancy.
8. Patients with a history of hypersensitivity or allergy to DPP-4 inhibitors.
9. Pregnant, lactating or postmenopausal women.
10. Patients who may need to add or discontinue concomitant medication or change the dose during the study period.
11. Patients who will require treatment with a prohibited concomitant medication during the study period.
12. Patients participating in other clinical studies.
13. Patients assessed ineligible in the study by the principal investigator or the investigator.

[Rationale for the exclusion criteria]

- 1, 10: These were set to exclude influences on senses of burden against treatment using concomitant medications including diabetic medications other than the allocated oral glucose-lowering medication.
- 2: This was set to exclude patients with type 1 diabetes, because the indications of trelagliptin and daily DPP-4 inhibitors are for "type 2 diabetes."
- 3: This was set to exclude patients with severe renal dysfunction or renal failure, because trelagliptin is contraindicated in such patients.
- 4-8, 11: These were set in consideration of patient safety.
- 9: This was set because trelagliptin should not be administered in pregnant or possibly pregnant females unless potential therapeutic benefits outweigh risks, and because excretion of trelagliptin and alogliptin into milk was observed in the non-clinical studies.
- 12, 13: These were set as fundamentals for this study.

7.3 Prohibited concomitant drugs and permitted concomitant drugs

The use of diabetic medications other than allocated oral glucose-lowering medication will be prohibited during from the start of the screening period (Week -4) until the end of the treatment period (Week 12).

<Rationale of prohibited concomitant drugs>

It was designed due to potential influences on the assessment of this clinical study.

7.4 Study subject management

The principal investigator and investigator shall instruct the research subject the items below.

- (1) Give instructions to take allocated oral hypoglycemic drug as directed.
- (2) If hypoglycemia symptom (hunger abnormal, feeling of weakness, trembling of hands and fingers, cold sweat, palpitations, etc.) is observed, take glucose or sucrose (sugar), and if it does not improve give instructions to visit promptly.
- (3) On visit days for planned laboratory tests, give instructions not to take oral hypoglycemic drug scheduled to be taken on that day. Further, at each visit, have the research subject report if drug has been taken or not the day before, and on the day of visit.
- (4) On visit days for planned laboratory tests, give instructions for fasting \geq 10 hours before visit (excluding start of observation period).
- (5) For research subjects of childbearing potential, give instructions to use adequate contraception. If pregnancy is discovered, have the research subject report promptly, and discontinue the research immediately.
- (6) The principal investigator and investigator shall instruct the research subject to adhere to instructed prohibited concomitant drugs. When drugs are taken other than the drugs prescribed by the principal investigator and investigator, have the research subject report its content.
- (7) Regarding subjective symptoms/objective findings, have the research subject report at visit the necessary items from its contents, onset date, degree, outcome and date of outcome.

7.5 Criteria for discontinuation or withdrawal of a study subject

The principal investigator or investigator shall record the main reason for discontinuation of protocol treatment on the case report form (CRF) according to the classification described below. Refer to Section 9.1.15 for study subjects who withdraw from the study before randomization.

1. Adverse events

When the study subject had an adverse event that requires withdrawal of the study subject from the study because continued participation in the study would impose an unacceptable risk to the

study subject's health, or when the study subject is unwilling to continue study participation because of the adverse event.

2. Major protocol deviation

When it is discovered after randomization that a study subject does not meet the eligibility criteria or is not adhering to the protocol, and continued participation in the study would impose an unacceptable risk to the study subject's health.

3. Lost to follow-up

When the study subject failed to make visits and could not be contacted despite the attempts to contact the study subject.

4. Voluntary termination

When the study subject wishes to withdraw from the study. The reason for discontinuation shall be obtained to the extent possible.

5. Study termination

When the sponsor or a committee such as the Ethical Review Board or regulatory authority has decided to terminate the study. Refer to Section 6.3.1 for details.

6. Pregnancy

When a female study subject was found to be pregnant.

Note: The study subject must discontinue the study immediately after she was found to be pregnant. Refer to Section 9.1.13 for the procedures.

7. Lack of efficacy

When efficacy of the study drug is not evident and continuation of the study may pose an unacceptable risk to the study subjects in the opinion of the principal investigator or investigator.

8. Others

When the principal investigator or investigator determined to terminate the study for other reasons.

The specific reasons should be recorded on the CRF.

7.6 Procedures for discontinuation of individual study subjects

The principal investigator or investigator shall terminate a study subject's study participation when the study subject meets the criteria described in Section 7.5. Individual study subjects may discontinue their study participation without giving a reason at any time during the study. Should a

study subject's participation be discontinued, the primary reason for termination shall be recorded on the CRF by the principal investigator or investigator. In addition, efforts shall be made to perform all tests/observations/evaluations scheduled at the time of discontinuation.

CONFIDENTIAL

8.0 STUDY TREATMENT

This section indicates the treatment regimen of this clinical research. See the latest package insert for details and handling of each drug.

8.1 Study drug and Comparative drug

8.1.1 Study drug

Generic name: Trelagliptin Succinate

Chemical name: 2-({6-[(3R)-3-Aminopiperidin-1-yl]-3-methyl-2, 4-dioxo-3, 4- dihydropyrimidin-1(2H)-yl}methyl)-4-fluorobenzonitrile monosuccinate

<Dose and administration method>

Trelagliptin: Trelagliptin 100 mg is orally administered once weekly. Trelagliptin 50 mg is orally administered once weekly in patients with moderate renal impairment.

8.1.2 Comparative drug

Daily DPP-4 inhibitor: Inhibitors shown in Table 8.a are orally administered at the dosage and administration instructed in the package inserts of each drug.

CONFIDENTIAL

Table 8.a Daily DPP-4 inhibitor

Inhibitors	Dosage and Administration
Sitagliptin: CCI	
Vildagliptin: CCI	
Alogliptin: CCI	
Linagliptin: CCI	
Teneligliptin: CCI	
Anagliptin: CCI	
Saxagliptin: CCI	Take orally in accordance with the instructions in the package inserts.

8.2 Overdose of the study drug

Overdose is defined as intentional or accidental administration of the study drug or comparative drug at a higher dose than that specified in the package inserts, either by a health professional or by the study subject.

To consistently collect important safety information about overdose, the principal investigator or investigator(s) shall record all cases of overdose on the “Overdose” page of the CRF, irrespective of the presence or absence of accompanying adverse event. Adverse events associated with overdose shall be recorded on the “Adverse events” page of the CRF, in accordance with the procedures described in Section 10.0, “Adverse Events.”

In addition, serious adverse events associated with overdose shall be recorded in accordance with the procedures described in Section 10.2.2, “Collection and reporting of serious adverse events.”

In the event of overdose, the principal investigator or investigator shall treat the subject as required based on symptoms.

8.3 Medication other than the study drug and the comparative drug

Prohibited concomitant drugs (refer to Section 7.3.1) may not be used. Other treatments shall be conducted under normal medical practice.

In principle, concomitant medications cannot be added or withdrawn, and the dosages of concomitant medications cannot be changed during this clinical study period (refer to the section 7.2). However, the addition of concomitant medications will be allowed as long as the principal investigator or investigator considers its necessity due to reasons such as adverse events. The principal investigator or investigator shall provide directions to study subjects not to take any medications (including over-the-counter drugs) other than the medications instructed to use without prior consultation.

8.4 Allocation of the study drug and administration procedure

The principal investigator or the designee shall access the Case Registration Web System to allocate the study subjects. The principal investigator or the designee shall notify the information required for allocation in addition to the study subject identification (ID) code. Then, drugs that should be administered to each study subject will be notified through the Case Registration Web System. The principal investigator or investigator shall prescribe the study drug or comparative drug according to the notification, and record the drug information (the name, dose per administration, number of daily administration and number of tablets per administration) into the CRF of each research subject.

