8.5 Preparation and storage of allocation list

The allocation responsible person (designated by the sponsor) shall create an allocation list.

Study subjects will be allocated at the Case Registration Center through the Case Registration Web System, using "the total score for the DTR-QOL Questionnaire [$<80\% (<168.2 \text{ as a score})$ or $\geq 80\% (\geq 168.2 \text{ as a score}^{\text{※}})$]" and "HbA1c ($<8.0\%$ or $\geq 8.0\%$)" at the start of the screening period as stratification factors. The Case Registration Center will use the allocation list for stratification prepared by the allocation responsible person in operating the treatment allocation.

※ Refer to the section 9.1.9 for the calculation method of the total score for the DTR-QOL Questionnaire.

Information on the allocation shall be kept in a safe place and shall not be available to anyone other than authorized persons, to secure independency from the clinical research.

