1.2.4 Dosing conditions of Study drug

Analysis Set: Full Analysis Set

Items: Trelagliptin (mg/week) [50, 100, Other]

Control Drugs [Sitagliptin, Vildagliptin, Alogliptin, Linagliptin, Teneligliptin, Anagliptin, Saxagliptin]

Control Drug(mg/day)

Sitagliptin [25, 50, 100, Other]

Vildagliptin [50, 100, Other]

Alogliptin	[25, Other]
Linagliptin	[5, Other]
Teneligliptin	[20, 40, Other]
Anagliptin	[200, 400, Other]
Saxagliptin	[2.5, 5, Other]

Method: (1) Frequency distribution at Week 0.

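### The control pools once- and twice-daily comparators with no choice declared before allocation, so the trial cannot test weekly against once-daily dosing on a randomised basis

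*Protocol*

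**What the plan says.** - **Design.** Protocol 6.1 describes a "multi-center, randomized, open-label, parallel-group comparison study to assess the reduction in treatment burden".
- **Comparator.** Protocol 8.1.2: "Inhibitors shown in Table 8.a are orally administered at the dosage and administration instructed in the package inserts of each drug". SAP 1.2.4 lists the same seven drugs ("Sitagliptin, Vildagliptin, Alogliptin, Linagliptin, Teneligliptin, Anagliptin, Saxagliptin"). Neither document gives a rule for choosing among them. The dosing column of Table 8.a is redacted in the public copy, and nothing here depends on it.
- **Allocation and prescription.** In Protocol 8.4 the site submits the information needed for allocation, which is not itemised. Then "drugs that should be administered to each study subject will be notified through the Case Registration Web System", and the investigator "shall prescribe the study drug or comparative drug according to the notification, and record the drug information", including the drug name and the number of daily administrations.
- **Stratification.** Protocol 8.5 uses the DTR-QOL total score and HbA1c "at the start of the screening period as stratification factors". Intended comparator and dosing frequency are not factors.
- **Primary analysis.** Protocol 13.1.3 and SAP 2.1 fit an ANCOVA with a single treatment-group term, so all daily inhibitors form one control.
- **Dosing frequency.** A planned grouping in Protocol 5.2.2 is "Number of doses of the study drug or comparative drug (once weekly, once daily or twice daily"). SAP 2.2, method (3), gives summary statistics and 95% confidence intervals for the mean change in each category, with no between-group contrast.
- **Premise.** Protocol 4.1 cites research in which "the level of compliance is decreased as dosing frequency increased", and expects fewer doses to help QOL and treatment satisfaction.

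**The concern.** The protocol's rationale is that dosing frequency drives treatment burden, and the primary outcome is a patient-reported score of that burden. The control arm nevertheless contains two dosing frequencies. A reader of a positive result will ask whether weekly dosing does better than once-daily dosing, or whether part of the difference comes from twice-daily controls.

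The plan's only tool for that question is the descriptive summary by frequency. Frequency varies only among controls, since every trelagliptin subject is once weekly. No document requires a record of which daily drug a trelagliptin subject would otherwise have received. Comparing once-daily controls with the whole trelagliptin arm would therefore set a selected part of one arm against all of the other. If prescribers match drug to patient, that comparison is no longer randomised, and a record made after an open allocation cannot restore it.

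**Working it through.** **1. The plan's own figures.** Inputs from Protocol 13.3: mean changes 19.0 and 14.4 (difference 4.6), SD 12.1, two-sided 5%, power 80%, 8% discontinuation.

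- n per group = 2 × [12.1 × (1.960 + 0.842) / 4.6]² = 108.6, so 109 by the normal approximation. The t-test version gives 109.58, so 110 as stated.
- 110 / 0.92 = 119.6, so 120 as stated.
- Power at 110 per group is 80.5%. The smallest significant difference is 1.960 × 12.1 × √(2/110) = 3.2 points.

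These figures reproduce and are not in dispute. The 14.4 is one mean for the whole daily group, so 4.6 is the assumed *pooled* difference.

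**2. How the mix enters the pooled contrast.** Let m_W, m_1 and m_2 be the mean changes under weekly, once-daily and twice-daily dosing, with g = m_1 − m_2, and let p be the share of controls on twice-daily drugs.

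- Control mean = (1 − p) m_1 + p (m_1 − g) = m_1 − p g
- Pooled difference = (m_W − m_1) + p g

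The pooled difference therefore exceeds the weekly-versus-once-daily difference by p × g. If g is negative, it falls short by the same rule.

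**3. Size over assumed ranges.** The documents give neither p nor g. The last column supposes that weekly and once-daily dosing do not differ at all. It is Φ(p g / SE − 1.960), with SE = √{[12.1² + 12.1² + p(1 − p)g²] / 110}.

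| g | p | p × g | Chance of a significant pooled result favouring trelagliptin |
|---|---|---|---|
| 2.3 | 10% | 0.23 | 3.4% |
| 2.3 | 25% | 0.58 | 5.4% |
| 2.3 | 50% | 1.15 | 10.4% |
| 4.6 | 10% | 0.46 | 4.7% |
| 4.6 | 25% | 1.15 | 10.4% |
| 4.6 | 50% | 2.30 | 28.7% |

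With p = 0 the last column would be 2.5%. Example for the last row: p(1 − p)g² = 0.25 × 21.16 = 5.29; SE = √[(146.41 + 146.41 + 5.29)/110] = 1.646; Φ(2.30/1.646 − 1.960) = 0.287. These are not type I error rates for the pooled comparison, because in each row the pooled means really do differ.

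**4. Reading 4.6 as the pooled difference, as Protocol 13.3 does.** The implied weekly-versus-once-daily difference is 4.6 − p g: 4.6 − 0.23 = 4.37 at the mild end and 4.6 − 2.30 = 2.30 at the strong end.

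**5. What a restricted analysis would cost.** Suppose 80% of declared comparators are once daily (an assumption): 0.80 × 110 = 88 per arm. SE = 12.1 × √(2/88) = 1.824, and power for 4.6 points = Φ(4.6/1.824 − 1.960) = Φ(0.562), about 71%. The 95% interval half-width is 1.960 × 1.824 = 3.6 points, against 3.2 with 110 per arm.

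**The case against.** **The pooled daily control is the stated comparator.** Protocol 4.2 and 6.2 compare trelagliptin with daily products in the plural, and 13.3 refers to DPP-4 inhibitors in current use. A twice-daily control belongs to that comparator, and a pooled usual-practice control is a legitimate choice. This stands: randomisation protects the pooled contrast, and its type I error is unaffected.

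**The mix will be visible.** SAP 1.2.4 tabulates drug and dose, SAP 1.2.1 tabulates dosing frequency, and SAP 2.2 gives the mean change by frequency. This also stands, but these tables describe the mix. They do not supply a randomised weekly-versus-once-daily contrast.

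**The comparator may not be chosen after allocation.** A reader might infer from Protocol 8.4 that a prescriber who already knows the subject is a control picks the drug. The text does not establish that. It says that drugs are notified, which could mean a named drug or only the group. The information submitted for allocation is not itemised and might include the intended comparator, and Protocol 1.2 leaves other administrative structures to separate documents. The supported statement is that selection is unspecified.

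**The primary result is not shown to be inflated by a known amount.** A reader might also assign the 4.6 points to once-daily dosing and scale burden linearly with doses per week: 4.6 × 13/6 = 9.97 against twice-daily dosing, hence pooled differences of 5.14, 5.67 and 6.75 (12%, 23% and 47% larger) at twice-daily shares of 10%, 20% and 40%. The documents do not support this. The 4.6 is already the pooled difference, its two means come from an SGLT2-inhibitor study and a questionnaire validation study rather than a dosing gradient, and no share is given.

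**Declaring the comparator beforehand would not change the pooled result.** Correct. Its value lies only in making a second, randomised comparison possible.

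**Conclusion.** The point holds as a gap in what the trial can show, not as a flaw in its primary test. The primary ANCOVA validly compares trelagliptin with whatever comparator mix is used. As written, the trial cannot say on a randomised basis whether an effect holds against once-daily dosing, because frequency is known only for controls and no pre-allocation declaration is required.

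The excess of the pooled difference over the weekly-versus-once-daily difference is p × g: 0.23 to 2.3 points over the assumed ranges, set against a planned difference of 4.6. That range rests entirely on assumed p and g. The sign rests on twice-daily drugs scoring lower, which follows the premise in Protocol 4.1 but has no figure behind it; a better-scoring comparator would shrink the contrast. This is a worthwhile, inexpensive improvement rather than a correction without which the primary result fails.

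**What to change.** - **Protocol 8.4 and 8.5.** State whether the notification names the drug or only the group. Require the site to record for every subject, before allocation is released, the daily DPP-4 inhibitor the investigator intends should the subject be a control, and its dosing frequency. The protocol need not say which drug to choose.
- **SAP 2.1.** Keep the pooled primary ANCOVA unchanged. Add the same model as a sensitivity analysis in subjects of both arms whose declared comparator is once daily. The declaration precedes randomisation in both arms, so the subset comparison stays randomised. Analyse by declared, not prescribed, comparator.
- **Reporting.** Base any weekly-versus-once-daily statement on that result, and label the existing summary by frequency as descriptive.

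The cost is one mandatory registration entry (drug and frequency) and one extra analysis. The subset has fewer subjects and a wider interval: about 71% power for 4.6 points if 88 of 110 per arm qualify, and less if fewer do. The entry has to be in place before subjects are allocated; it cannot be rebuilt without bias afterwards.
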